## 3.2. Secondary Endpoints

### 3.2.1. Secondary Immunogenicity Endpoints

The persistence of the immune response to 2 or 3 doses of 100 µg mRNA-1273, as assessed by the level of anti-SARS-CoV-2 S-specific bAb through 1 year after dose 2 or dose 3 will be evaluated by the following endpoints:

- For all unvaccinated participants, the geometric mean (GM) value of anti-SARS-CoV-2 S-specific bAb on Day 1, Day 29 (28 days after dose 1), and Day 57 (28 days after dose 2)
  - For participants receiving the 2-dose regimen, GM will be evaluated on Day 209 (6 months after dose 2), and Day 394 (1 year after dose 2)
  - For participants receiving the 3-dose regimen, GM will be evaluated on Day 85 (dose 3), Day 113 (28 days after dose 3), Day 265 (6 months after dose 3), and Day 450 (1 year after dose 3)
- For all previously vaccinated with 2 doses of Moderna COVID-19 vaccine SOT recipients, GM will be evaluated on Day 1 (dose 3), Day 29 (28 days after dose 3), Day 180 (6 months after dose 3), and Day 365 (1 year after dose 3)
- For all unvaccinated participants, the geometric mean fold rise (GMFR) of bAb relative to Day 1 on Day 29 (28 days after dose 1), and Day 57 (28 days after dose 2)

- For participants receiving the 2-dose regimen, GMFR will be evaluated on Day 209 (6 months after dose 2), and Day 394 (1 year after dose 2)
- For participants in the 3-dose regimen, GMFR will be evaluated on Day 85 (dose 3), Day 113 (28 days after dose 3), Day 265 (6 months after dose 3), and Day 450 (1 year after dose 3)
- For all previously vaccinated with 2 doses of Moderna COVID-19 vaccine SOT recipients, GMFR of bAb relative to Day 1 (dose 3) will be evaluated on Day 29 (28 days after dose 3), Day 180 (6 months after dose 3), and Day 365 (1 year after dose 3)

The persistence of the immune response to 2 or 3 doses of 100 µg mRNA-1273, as assessed by the level of nAb through 1 year after dose 2 or dose 3 will be evaluated by the following endpoints:

- For all unvaccinated participants, the GMCs of SARS-CoV-2-specific nAb on Day 1 and Day 29 (28 days after dose 1)
  - For participants in the 2-dose regimen, GMC will be evaluated on Day 209 (6 months after dose 2) and Day 394 (1 year after dose 2)
  - For participants in the 3-dose regimen, GMC will be evaluated on Day 85 (dose 3), Day 113 (28 days after dose 3), Day 265 (6 months after dose 3), and Day 450 (1 year after dose 3)
- For all previously vaccinated with 2 doses of Moderna COVID-19 vaccine SOT recipients, GMCs of SARS-CoV-2-specific nAb will be evaluated on Day 1 (dose 3), Day 29 (28 days after dose 3), Day 180 (6 months after dose 3), and Day 365 (1 year after dose 3)
- For all unvaccinated participants, GMFR of nAb relative to Day 1 will be evaluated on Day 29 (28 days after dose 1) and Day 57 (28 days after dose 2)
  - For participants receiving the 2-dose regimen, GMFR will be evaluated on Day 209 (6 months after dose 2), and Day 394 (1 year after dose 2).
  - For participants in the 3-dose regimen, GMFR will be evaluated on Day 85 (dose 3), Day 113 (28 days after dose 3), Day 265 (6 months after dose 3), and Day 450 (1 year after dose 3).
- For all previously vaccinated with 2 doses of Moderna COVID-19 vaccine SOT recipients, GMFR of nAb relative to Day 1 (dose 3) will be evaluated on Day 29 (28 days after dose 3), Day 180 (6 months after dose 3), and Day 365 (1 year after dose 3).

### 3.2.2. Secondary COVID-19 and SARS-CoV-2 Infection Endpoints

The incidence of asymptomatic SARS-CoV-2 infection after mRNA-1273 vaccination in adult SOT recipients and healthy adult participants with negative SARS-CoV-2 at baseline will be evaluated by the following endpoints:

The incidence of asymptomatic SARS-CoV-2 infection among recipients of mRNA-1273 SARS-CoV-2 vaccine will be defined in participants with negative SARS-CoV-2 at baseline as:

- bAb levels against SARS-CoV-2 nucleocapsid protein negative (as measured by Roche Elecsys) at Day 1 that become positive (as measured by Roche Elecsys) counted starting 28 days after the second dose and 28 days after the third dose of vaccine, OR
- Positive reverse transcriptase polymerase chain reaction (RT-PCR) (central lab or local diagnostic tests) counted starting 14 days after the second and after the third dose of vaccine

The incidence of COVID-19 after vaccination with mRNA-1273 in SOT recipients and healthy participants will be evaluated by the following endpoints:

- First occurrence of COVID-19 starting 14 days after the second dose and after the third dose of vaccine, where COVID-19 is defined as symptomatic disease based on the following criteria:
  - The participant must have experienced at least TWO of the following symptoms: fever ( $\geq 38^{\circ}\text{C}/\geq 100.4^{\circ}\text{F}$ ), chills, myalgia, headache, sore throat, or new olfactory and taste disorder(s), OR
  - The participant must have experienced at least ONE of the following respiratory signs/symptoms: cough, shortness of breath or difficulty breathing, OR clinical or radiographical evidence of pneumonia, AND
  - The participant must have at least 1 nasopharyngeal (NP) swab, nasal swab, or saliva sample (or respiratory sample, if hospitalized) positive for SARS-CoV-2 by RT-PCR
- First occurrence of severe COVID-19 starting 14 days after the second dose and after the third dose of vaccine, where severe COVID-19 is defined as symptomatic COVID-19 AND any of the following:
  - Clinical signs indicative of severe systemic illness, respiratory rate  $\geq 30$  per minute, heart rate  $\geq 125$  beats per minute, oxygen saturation ( $\text{SpO}_2$ )  $\leq 93\%$  on room air at sea level, or partial pressure of oxygen ( $\text{PaO}_2$ )/fraction of inspired oxygen ( $\text{FIO}_2$ )  $< 300$  mm Hg, OR

- Respiratory failure or acute respiratory distress syndrome (ARDS, defined as needing high-flow oxygen, noninvasive or mechanical ventilation, or extracorporeal membrane oxygenation) or evidence of shock (systolic blood pressure [BP] < 90 mm Hg, diastolic BP < 60 mm Hg, or requiring vasopressors), OR
  - Significant acute renal, hepatic, or neurologic dysfunction, OR
  - Admission to an intensive care unit or death.
- The secondary case definition of COVID-19 is defined as the following symptoms:
  - Fever (temperature  $\geq 38^{\circ}\text{C}$ ) or chills, cough, shortness of breath or difficulty breathing, fatigue, muscle aches or body aches, headache, new loss of taste or smell, sore throat, nasal congestion or rhinorrhea, nausea or vomiting or diarrhea AND
  - A positive NP swab, nasal swab, or saliva sample (or respiratory sample, if hospitalized) for SARS-CoV-2 by RT-PCR.

### **3.2.3. Secondary Transplant Impact Endpoints**

The changes in liver and renal function through laboratory tests over time in SOT recipients after vaccination with mRNA-1273 vaccine will be evaluated by the following endpoints:

- Safety laboratory assessments of kidney (serum creatinine, urine protein, and urine protein to creatinine ratio [UPCR]) and liver (alanine aminotransferase [ALT], aspartate aminotransferase [AST], alkaline phosphatase [ALP], and bilirubin) function:
  - For unvaccinated SOT recipients, from Day 1 through Day 57 for SOT recipients who receive 2 doses and through Day 113 for SOT recipients who receive 3 doses of mRNA-1273.
  - For previously vaccinated with 2 doses of Moderna COVID-19 vaccine SOT recipients, from Day 1 (dose 3) through Day 29 (28 days after dose 3).

The changes in immunosuppressant medications in SOT recipients after vaccination with mRNA-1273 vaccine will be evaluated by the following endpoints:

- Change in immunosuppressant medications to treat organ transplant rejection or to improve immune tolerance from Day 1 and throughout the study period. Change in immunosuppressant medication is defined as any of the following:
  - Any adjustments (temporarily or permanently) in immunosuppressants, OR
  - Addition of new immunosuppressants, OR
  - Switching from 1 maintenance rejection prophylaxis regimen to another.

### 3.3. Exploratory Endpoints

The exploratory endpoints of 100 µg mRNA-1273 administered in 2-dose or 3-dose regimens are the following:

- Comparison of genetic sequence of viral isolates with that of the vaccine sequence
- Description of clinical severity and immune responses of participants who are identified as infected by SARS-CoV-2 or having COVID-19
- GM and GMFR of bAb levels against SARS-CoV-2 nucleocapsid protein (quantitative immunoglobulin G [IgG]) and percent of study participants with 2×, 3×, and 4× rise of bAb relative to baseline
- Magnitude, phenotype, and percentage of cytokine producing S protein-specific T-cells as measured by flow cytometry at Day 1, Day 36, and Day 92 for unvaccinated SOT recipients, at Day 1 and Day 8 for previously vaccinated SOT recipients, and at Day 1 and Day 36 in healthy participants
- Magnitude and phenotype of S protein-specific B-cells as measured by flow cytometry at Day 1, Day 36, and Day 92 for unvaccinated SOT recipients, at Day 1 and Day 8 for previously vaccinated SOT recipients, and at Day 1 and Day 36 in healthy participants
- Determination of targeted major antigenic sites and amino acid residues on SARS-CoV-2 S protein

The exploratory endpoints of 100 µg BD of mRNA-1273 are the following:

- The GM value of SARS-CoV-2 S2P specific bAb on BD-Day 1, BD-Day 29 (28 days after BD), and BD-Day 181 (6 months after BD)
- The GM values of SARS-CoV-2-specific nAb on BD-Day 1, BD-Day 29 (28 days after BD), and BD-Day 181 (6 months after BD)

The incidence of asymptomatic SARS-CoV-2 infection after BD with mRNA-1273 vaccination in adult SOT recipients and healthy adult participants with negative SARS-CoV-2 at baseline will be evaluated by the following endpoints:

- bAb levels against SARS-CoV-2 nucleocapsid protein negative (as measured by Roche Elecsys) at Day 1 that become positive (as measured by Roche Elecsys) counted starting 28 days after the BD, OR
- Positive RT-PCR counted starting 14 days after the BD

The incidence of COVID-19 after BD with mRNA-1273 in SOT recipients and healthy participants will be evaluated by the following endpoints:

- First occurrence of COVID-19 starting 14 days after BD, where COVID-19 is defined as symptomatic disease based on the following criteria:
  - The participant must have experienced at least TWO of the following symptoms: fever ( $\geq 38^{\circ}\text{C}/\geq 100.4^{\circ}\text{F}$ ), chills, myalgia, headache, sore throat, or new olfactory and taste disorder(s), OR
  - The participant must have experienced at least ONE of the following respiratory signs/symptoms: cough, shortness of breath or difficulty breathing, OR clinical or radiographical evidence of pneumonia, AND
  - The participant must have at least 1 NP swab, nasal swab, or saliva sample (or respiratory sample, if hospitalized) positive for SARS-CoV-2 by RT-PCR
- First occurrence of severe COVID-19 starting 14 days after the BD, where severe COVID-19 is defined as symptomatic COVID-19 AND any of the following:
  - Clinical signs indicative of severe systemic illness, respiratory rate  $\geq 30$  per minute, heart rate  $\geq 125$  beats per minute,  $\text{SpO}_2 \leq 93\%$  on room air at sea level, or  $\text{PaO}_2/\text{FIO}_2 < 300$  mm Hg, OR
  - ARDS, defined as needing high-flow oxygen, noninvasive or mechanical ventilation, or extracorporeal membrane oxygenation, or evidence of shock (systolic BP  $< 90$  mm Hg, diastolic BP  $< 60$  mm Hg, or requiring vasopressors), OR
  - Significant acute renal, hepatic, or neurologic dysfunction, OR
  - Admission to an intensive care unit or death.
- The secondary case definition of COVID-19 is defined as the following symptoms:
  - Fever (temperature  $\geq 38^{\circ}\text{C}$ ) or chills, cough, shortness of breath or difficulty breathing, fatigue, muscle aches or body aches, headache, new loss of taste or smell, sore throat, nasal congestion or rhinorrhea, nausea or vomiting or diarrhea, AND
  - A positive NP swab, nasal swab, or saliva sample (or respiratory sample, if hospitalized) for SARS-CoV-2 by RT-PCR.

The changes in liver and renal function through laboratory tests over time in SOT recipients after BD with mRNA-1273 vaccine will be evaluated by the following endpoints:

- Safety laboratory assessments of kidney (serum creatinine, urine protein, and UPCR) and liver (ALT, AST, ALP, and bilirubin) function from BD-Day 1 through BD-Day 29 (28 days after BD):

The changes in immunosuppressant medications in SOT recipients after BD with mRNA-1273 vaccine will be evaluated by the following endpoints:

- Change in immunosuppressant medications to treat organ transplant rejection or to improve immune tolerance from BD-Day 1 and throughout the study period. Change in immunosuppressant medication is defined as any of the following:
  - Any adjustments (temporarily or permanently) in immunosuppressants, OR
  - Addition of new immunosuppressants, OR
  - Switching from 1 maintenance rejection prophylaxis regimen to another.

The genetic and/or phenotypic relationships of isolated SARS-CoV-2 strains to the vaccine sequence will be evaluated by the following endpoints:

- Comparison of genetic sequence of viral isolates with that of the vaccine sequence

The clinical profile and immune responses of participants with COVID-19 or with SARS-CoV-2 infection; and to describe the incidence of asymptomatic SARS-CoV-2 infection after mRNA-1273 vaccination in adult SOT recipients and healthy adult participants with serologic evidence of infection at baseline after BD with mRNA-1273 vaccine will be evaluated by the following endpoints:

- Description of clinical severity and immune responses of participants who are identified as infected by SARS-CoV-2 or having COVID-19
- GM and GMFR of bAb levels against SARS-CoV-2 nucleocapsid protein (IgG) and percent of study participants with 2 $\times$ , 3 $\times$ , and 4 $\times$  rise of bAb relative to baseline

The SARS-CoV-2 S protein-specific T-cell responses and the epitopes recognized by B-cell and antibodies responses in a subset of SOT recipients and healthy participants who received BD will be evaluated by the following endpoints:

- Magnitude, phenotype, and percentage of cytokine producing S protein-specific T cells at BD-Day 1 and BD-Day 8
- Magnitude and phenotype of S protein specific B cells as measured by flow cytometry at BD-Day 1 and BD-Day 8
- Determination of targeted major antigenic sites and amino acid residues on SARS-CoV-2 S protein

## 4. Study Design

### 4.1. Overall Study Design

This is a Phase 3b, open-label study to evaluate the safety, reactogenicity, and immunogenicity of mRNA-1273 SARS-CoV-2 vaccine in SOT recipients and healthy controls. Adult kidney and liver transplant recipients and healthy control participants who are at least 18 years of age will be enrolled at ~20 sites in US and non-US sites.

Approximately 240 adult participants (220 previously vaccinated or unvaccinated participants who have had a kidney or liver transplant and 20 unvaccinated healthy adults) will be enrolled. At least 50 SOT recipients who completed primary series vaccines with mRNA or non-mRNA COVID-19 vaccine under EUA outside the study will be enrolled in Part B (Group B4).

[figure not shown]
In Part A, all SOT recipients who were unvaccinated prior to enrollment will receive 2 doses of 100  $\mu$ g of mRNA-1273 (vaccine) 28 days apart (window of -3/+7 days for the second dose) (Group A1). The SOT recipients will be offered the opportunity to receive a third dose of vaccine at Day 85 (window of -3/+7 days for the third dose) (Group A2). All healthy participants will receive 2 doses of vaccine 28 days apart (window of -3/+7 days for the second dose) (Group A5). SOT recipients who were previously vaccinated with 2 doses of Moderna COVID-19 vaccine under the EUA prior to enrollment will receive dose 3 on Day 1 (Group A3). These participants will be referred to as previously vaccinated throughout this document.

Under Amendment 4, unvaccinated SOT participants who will be enrolled will be given 3 100  $\mu$ g doses in Part A then proceed to Part B to receive a 100  $\mu$ g booster dose (Group A2 to Group B2). SOT participants previously vaccinated with 2 doses of Moderna COVID-19 vaccine outside of the study who will be enrolled will receive a third 100  $\mu$ g dose in Part A then proceed to Part B to receive a 100  $\mu$ g BD (Group A3 to Group B3). SOT participants who completed primary series vaccines with mRNA or non-mRNA COVID-19 vaccine outside of the study who consent to receive 1 booster dose in Part B (Group B4). Healthy participants who will be enrolled will be given 2 100  $\mu$ g doses in Part A then proceed to Part B to receive a 100  $\mu$ g booster dose (Group A5 to Group B5).

In Part B, all eligible active participants in Part A will be offered to receive a 100  $\mu$ g BD of mRNA-1273 who are at least 4 months from the last dose.

[figure not shown]
The schematic of study arms and major study events is illustrated in [Figure 1](#), [Figure 2](#), [Figure 3](#), and [Figure 4](#). The schedules of events for the study are presented in Section 10.1 of Protocol Amendment 4. Study arms and doses are presented in **Error! Reference source not found.** of Protocol Amendment 4.

**Figure 1. Study Schema for Unvaccinated Participants Who Receive the 2-Dose Vaccination Regimen (Part A)**

[figure not shown]
Abbreviations: CMI = cell-mediated immunity; IA = interim analysis; immuno = immunogenicity; NP = nasopharyngeal; SOT = solid organ transplant (recipients).

**Figure 2. Study Schema for Unvaccinated Participants Who Receive the 3-Dose Vaccination Regimen (Part A)**

[figure not shown]
Abbreviations: CMI = cell-mediated immunity; NP = nasopharyngeal; SOT = solid organ transplant (recipients).

**Figure 3. Study Schema for Previously Vaccinated Participants Who Receive a Single-dose Vaccination Regimen (dose 3) (Part A)**

Abbreviations: CMI = cell-mediated immunity; NP = nasopharyngeal; SOT = solid organ transplant.

**Figure 4. Study Schema for Booster Dose Phase (Part B)**

## 4.2. Sample Size and Power

The study vaccine, mRNA-1273, is currently being evaluated in a pivotal Phase 3 efficacy, safety, and immunogenicity study in an adult population at high risk of COVID-19 disease (Study P301). Success criteria for early efficacy was met at the first interim analysis based on 95 adjudicated cases with a vaccine efficacy of 94.5% (95% CI: 86.5%, 97.8%; one-sided p value < 0.0001 of testing the null hypothesis of  $VE \leq 30\%$ ). Study P301 is expected to provide immunogenicity data by which an Ab threshold of protection against COVID-19 will be estimated.

This current study, which aims to evaluate Ab responses following a second dose of mRNA-1273 vaccine among kidney and liver transplant recipients, is expected to provide clinical data to determine whether this cohort of immunocompromised participants has immune responses following vaccination comparable to those of the participants in Study P301 and comparable to those of the concurrently assessed cohort of participants in this study with normal immune function.

With 200 SOT participants, if the true AE rate of biopsy-proven organ rejection is 3%, there is approximately >95% probability to observe at least 1 subject reporting such an AE.

The planned sample size of approximately 240 participants (220 unvaccinated or previously vaccinated participants who have had a kidney or liver transplant and 20 unvaccinated healthy participants) who receive 2-dose and 3-dose regimens of 100  $\mu$ g of mRNA 1273, or 100  $\mu$ g BD regimen are expected to provide useful estimates of Ab response at Day 29 for previously vaccinated SOT recipients who receive dose 3 in Part A, and Day 113 for unvaccinated SOT recipients who receive the 3-dose regimen, at Day 57 for unvaccinated participants who receive the 2-dose regimen, and at BD-Day 29 for Part B participants who receive a BD (primary endpoints), respectively, for comparison to results from Study P301 (if available at the time of database lock). The healthy adult participants will be used primarily as a biological control for the CMI analysis. This study is designed for estimation purposes, and no between-group comparisons are planned.

## 4.3. Randomization

No randomization will be used in this study, as it is open-label and only a single intervention (100  $\mu$ g mRNA-1273) is used for both primary series and BD.

## 4.4. Blinding and Unblinding

No blinding or unblinding will be performed as the study is open-label.  
Confidential

## 5. Analysis Populations

The following analysis sets are defined for Part A and Part B: Full Analysis/Safety Set, Modified Intent-to-Treat Set, Modified Intent-to-Treat-1 Set, Per-Protocol Set, Per-Protocol Immunogenicity Set, and Solicited Safety Set. Part A and Part B will share the same definition for Full Analysis/Safety Set and Solicited Safety Set.

### 5.1. Full Analysis/Safety Set

The Full Analysis/Safety Set consists of all participants who received at least one dose of IP in each part. SOT recipients who completed primary series vaccination with an mRNA or non-mRNA COVID-19 vaccine outside of the study will be included in the Full Analysis/Safety Set if received BD. The Safety Set is identical to the Full Analysis Set defined in the protocol. The Safety Set will be used for all analyses of safety except for the solicited ARs.

### 5.2. Analysis Population for Part A

All participants who are enrolled in Part A will be considered into analysis populations for Part A regardless of whether participants continue to Part B.

#### 5.2.1. Modified Intent-to-Treat Set (Part A)

The Modified Intent-to-Treat (mITT) Set (Part A) includes all participants in Safety Set who had no immunologic or virologic evidence of prior COVID-19 (ie, negative RT-PCR test and bAb against SARS-CoV-2 nucleocapsid (as measured by Roche Elecsys Anti-SARS-CoV-2 assay) below limit of detection [LOD] or lower limit of quantification [LLOQ]) at baseline/pre-vaccination before the first dose of IP.

#### 5.2.2. Per-Protocol Set (Part A)

The Per-Protocol (PP) Set (Part A) includes all participants in the mITT set (Part A) who received planned doses of study vaccination per schedule and had no major protocol deviations that impact key or critical data.

#### 5.2.3. Per-Protocol Immunogenicity Set (Part A)

The PP Immunogenicity Set (Part A) includes all participants in the mITT Set (Part A) who received planned doses of study vaccination per schedule, complied with the timings of immunogenicity blood sampling to have post-injection results available for at least one assay component corresponding to the immunogenicity analysis objective, and participant Confidential

had no major protocol deviations that impact immune response during the period corresponding to the immunogenicity analysis objective.

The PP Immunogenicity Set (Part A) will serve as the primary analysis population for the analysis of SARS-CoV-2-specific bAb and nAb immunogenicity data in Part A.

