With SARS-CoV-2 expected to be circulating in the general population during the study, all participants will provide pre- and post-dose blood samples for Ab analysis through 12 months after the last dose of vaccine in Part A or through 6 months after the BD in Part B. In addition, in Part A, unvaccinated participants will have NP swab samples collected, before the injections on Day 1 and Day 29, and on Day 57 for those receiving the 2-dose regimen, before injections on Day 1, Day 29, and Day 85, and on Day 57, and Day 113 for those receiving the 3-dose regimen, and before injection on Day 1 and on Day 29 for previously vaccinated SOT recipients who receive dose 3. In Part B, NP swabs will be collected before BD injection on BD-D1. Furthermore, with any signs or symptoms or MAAE suggesting SARS-CoV-2 infection in a participant, an additional nasal or NP swab sample and a blood sample will be taken to confirm the diagnosis of SARS-CoV-2 via serology and RT-PCR. Additionally, clinical information will be carefully collected to evaluate the severity of the clinical case.

As it is possible that participants are naturally exposed to SARS-CoV-2 through community exposure, the NP and/or nasal swab samples collected before study injection and the serologic assays for Ab responses to nonvaccine antigen(s) may help discriminate between natural infection and vaccine-induced Ab responses, should such discrimination be needed.

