8.2. Analyses Sets

The analysis sets are defined in [Table 5](#).

Table 5: Analysis Sets

Analysis Set	Description
Full Analysis Set (FAS)	All participants who received at least 1 dose of vaccine.
Modified Intent-to-Treat Set (mITT)	All participants who have negative SARS-CoV-2 status at baseline, defined as who have a negative RT-PCR test for SARS-CoV-2 and a negative serology test based on bAb specific to SARS-CoV-2 nucleocapsid protein (as measured by Roche Elecsys Anti-SARS-CoV-2 assay) at baseline.
PP Subset	All participants in the mITT set who receive all planned doses of study vaccination per schedule and have no major protocol deviations that impact key or critical data.
PP Immunogenicity Subset	All participants who received planned doses of study vaccination per schedule, complied with immunogenicity testing schedule, and have no major protocol deviations that impact key or critical data. Participants who are seropositive at baseline will be excluded from the PP Immunogenicity Subset. The PP Immunogenicity Subset will be used for analyses of immunogenicity unless specified otherwise. The PP Immunogenicity Set will serve as the primary population for the analysis of SARS-CoV-2-specific bAb and nAb immunogenicity data.
Solicited Safety Set	All participants in the FAS who contributed any solicited AR data. The Solicited Safety Set will be used for the analyses of solicited ARs.
Safety Set	All participants who receive at least 1 dose of vaccine. The Safety Set will be used for all analyses of safety except for the solicited ARs.

Abbreviations: AR = adverse reaction; bAb = binding antibody; nAb = neutralizing antibody; RT-PCR = reverse transcriptase polymerase chain reaction; SARS-CoV-2 = Severe Acute Respiratory Syndrome coronavirus 2; vaccine = investigational product.

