#### **5.3.1. Modified Intent-to-Treat Set (Part B)**

The mITT Set (Part B) consists of all participants in the Safety Set who received BD and had no immunologic or virologic evidence of prior COVID-19 (ie, negative RT-PCR test and bAb against SARS-CoV-2 nucleocapsid (as measured by Roche Elecsys Anti-SARS-CoV-2 assay)) below LOD or LLOQ at pre-booster before the BD.

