#### **5.3.3. Per-Protocol Immunogenicity Set (Part B)**

PP Immunogenicity Set (Part B) includes all participants in the mITT Set (Part B) who received planned BD per schedule, and SOT recipients who completed primary series vaccination with an mRNA or non-mRNA COVID-19 vaccine outside of the study that are in the mITT Set (Part B). The participants who complied with the timings of immunogenicity blood sampling to have post-booster results available for at least one assay component corresponding to the immunogenicity analysis objective, and participant had no major protocol deviations that impact immune response during the period corresponding to the immunogenicity analysis objective will be included.

The PP Immunogenicity Set (Part B) will serve as the primary analysis population for the analysis of SARS CoV 2-specific bAb and nAb immunogenicity data in Part B.

Confidential

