### **6.4. Immunogenicity Analysis**

Immunogenicity samples will be collected at baseline and post-baseline visits, as described in the Schedule of Events in Appendix 1 of Protocol Amendment 4. The PP Immunogenicity Set (Part A/Part B) is the primary analysis population used in the immunogenicity analyses, unless otherwise specified. The mITT set (Part A/Part B) will be used for sensitivity analyses. Concomitant medications and/or vaccines received during the study as described in Section 5.5.3 in Protocol Amendment 4 and Protocol Clarification Memorandum 11 as well as antiretroviral treatments that impact neutralizing antibody responses may be used to determine subject's immunogenicity samples that are eligible for the immunogenicity analyses. Participants will be summarized according to participant group as defined in [Section 6.1](#).

Confidential

The GM levels will be calculated using the following formula:

$$10^{\left\{ \frac{\sum_{i=1}^n \log_{10}(t_i)}{n} \right\}}$$

where  $t_1, t_2, \dots, t_n$  are  $n$  observed immunogenicity levels.

The GMFR measures the changes in immunogenicity levels within subjects. The GMFR will be calculated using the following formula:

$$10^{\left\{ \frac{\sum_{i=1}^n \log_{10}\left(\frac{v_{ij}}{v_{ik}}\right)}{n} \right\}} = 10^{\left\{ \frac{\sum_{i=1}^n \log_{10}(v_{ij}) - \log_{10}(v_{ik})}{n} \right\}}$$

where, for  $n$  subjects,  $v_{ij}$  and  $v_{ik}$  are observed immunogenicity levels for subject  $i$  at time points  $j$  and  $k$ ,  $j \neq k$

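### The SAP has no rule for SARS-CoV-2 infection after the baseline or pre-booster screen, so titres taken after an infection enter the immunogenicity summaries, mainly affecting persistence

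*SAP*

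**What the plan says.** The Part A set starts from an mITT set limited to participants "who had no immunologic or virologic evidence of prior COVID-19", judged "at baseline/pre-vaccination before the first dose of IP" (SAP 5.2.1). The Part B parent set applies the same screen "at pre-booster before the BD" (SAP 5.3.1). Protocol 8.2 is no wider: "Participants who are seropositive at baseline will be excluded from the PP Immunogenicity Subset".

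Beyond that screen, SAP 5.2.3 and 5.3.3 require dosing per schedule, compliant sampling with a result, and no relevant deviation. The Part A wording is "had no major protocol deviations that impact immune response during the period corresponding to the immunogenicity analysis objective", and Part B repeats it. SAP 6.2.7 leaves the major-deviation rules to be written before database lock.

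SAP 6.4 adds an optional sample-level rule. Concomitant medications and vaccines (by reference to Protocol 5.5.3 and Clarification Memorandum 11) "as well as antiretroviral treatments that impact neutralizing antibody responses may be used to determine" which samples are eligible. Protocol 5.5.3 lists products, not infection. SAP 6.4 also names the mITT sets for sensitivity analyses.

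Protocol 3.2 recognises the issue: swabs taken before injection and serology to nonvaccine antigens "may help discriminate between natural infection and vaccine-induced Ab responses", if that is needed. Neither document turns this into an analysis rule. SAP 6.5.2 provides listings of antibody levels for infected participants, and SAP 6.6 allows descriptive summaries of them.

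**The concern.** The secondary objective in Part A is persistence of the response to 2 or 3 vaccine doses through one year. The plan removes antibody due to infection at the start but not later, during follow-up in which the protocol expects the virus to circulate. A participant infected in month 4 can contribute a high titre at month 6 or 12, and the summary would credit it to the vaccine. Waning would then look slower than it is. A participant who did not respond to vaccine could also be counted as a seroresponder after infection (SAP 6.4.3.1).

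Infection is not obviously a protocol deviation. Protocol 10.2.8 treats deviations as noncompliance by the participant, the investigator or site staff, whereas infection is a study endpoint with its own analysis in SAP 6.5.

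**Working it through.** The plan states no figure on this point, so there is none to reproduce. The check has three parts.

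**1. Does any rule remove a sample taken after infection?**

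- mITT screens (SAP 5.2.1, 5.3.1): before dose 1 or before the booster only.
- Dosing and sampling conditions (5.2.3, 5.3.3): not about infection.
- Major deviations (6.2.7): rules deferred; infection not named.
- Sample eligibility (6.4, Protocol 5.5.3): optional, and triggered by treatments and vaccines.
- Summaries (6.4.2, 6.4.3, 6.4.3.1): produced by time point, with no censoring at infection.

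No rule is found. Each PP Immunogenicity Set is drawn from its mITT set, so the mITT sensitivity analysis contains the same post-infection samples.

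**2. How long can an infection go unscreened before each sample?** Nominal sample day minus day of the last infection screen that governs the set:

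| Sample | Screen | Days |
|---|---|---|
| Group A3, Day 29 | Day 1 | 29 − 1 = 28 |
| BD-Day 29 | BD-Day 1 | 29 − 1 = 28 |
| 2-dose, Day 57 | Day 1 | 57 − 1 = 56 |
| 3-dose, Day 113 | Day 1 | 113 − 1 = 112 |
| BD-Day 181 | BD-Day 1 | 181 − 1 = 180 |
| Group A3, Days 180 and 365 | Day 1 | 179 and 364 |
| 2-dose, Days 209 and 394 | Day 1 | 208 and 393 |
| 3-dose, Days 265 and 450 | Day 1 | 264 and 449 |

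The 6- and 12-month Part A rows concern unboosted participants. Participants who take the booster move to the Part B schedule, and SAP Table 3 gives boosted regimens no 6- or 12-month Part A immunogenicity window.

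**3. What size could it have?** Let p be the share of the set infected before the sample and R the multiple by which infection raises their titre. If the infected otherwise resemble the rest, the mean log10 titre rises by p × log10(R), so the GMC is multiplied by R^p. The documents give neither p nor R; both are assumed, with no waning of the infection boost. For R, 4 is the SAP seroresponse threshold, 10 is a middle value, and 37 is a rise after vaccine boosting in another study (Protocol 1.2.2), used only as a high value.

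| p | R = 4 | R = 10 | R = 37 |
|---|---|---|---|
| 2% | 1.03 | 1.05 | 1.07 |
| 10% | 1.15 | 1.26 | 1.43 |
| 20% | 1.32 | 1.58 | 2.06 |

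For persistence with R = 10, a true fall to 50% of peak reads as 0.50 × 1.26 = 63% at p = 10%, and as 0.50 × 1.58 = 79% at p = 20%.

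For a response rate s, the upper bound is s + p(1 − s), which assumes that every infected non-responder crosses the threshold. Taking s from the 30–60% antibody detection after 2 doses in Protocol 1.1 (not the SAP seroresponse definition, so also an assumption), at p = 10%: 0.30 + 0.10 × 0.70 = 37%, and 0.60 + 0.10 × 0.40 = 64%.

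**The case against.** The strongest reply is that two governing texts are not available: Clarification Memorandum 11 and the final major-deviation rules. Either might deal with infection. This stands as a limit. The point is about the SAP as shown, and a reader should not infer that the sponsor has decided to keep these samples. However, the SAP cites the memorandum only in a sentence about medications and vaccines.

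Some handling already exists, and this also stands:

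- Infections before the booster are removed from the Part B sets, so only later ones remain there.
- Infected participants given monoclonal antibodies or immunoglobulins may lose samples, though because of the treatment.
- An infection before a later Part A dose may lead the investigator to withhold that dose (Protocol 6.2), which would take the participant out of the set. That is discretionary and does not touch infections after the last dose.
- Titres of infected participants will be listed. A listing does not correct a GMC.

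A reader might infer that the primary 28-day endpoints are seriously biased. The documents do not support that. Group A3 Day 29 and BD-Day 29 follow a negative screen by about 28 days; if 1–2% were infected (assumed), the range 4- to 37-fold gives 1.01 to 1.07. Days 57 and 113 have longer exposure, about 56 and 112 days, but still much less than the late visits.

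A reader might also infer distorted group comparisons. SAP 4.2 plans none, although Protocol 8.3.3 sets results against healthy participants and Study P301, and SAP 6.4.3.1 says seroresponse differences may be given.

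Finally, censoring is not neutral. If participants with low titres are infected more often, removing their later samples could itself raise late GMCs. That is a good reason to report both versions.

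**Conclusion.** The point holds as an omission with a predictable direction. As shown, the SAP states no rule for infection after the screen, so following it mixes infection-derived antibody into the GMC, GMFR and seroresponse summaries, and the planned sensitivity analysis cannot reveal it. The consequence is greatest for the 6- and 12-month samples of unboosted Part A participants (a secondary objective) and for BD-Day 181 (exploratory). It is smaller at Days 57 and 113 and minor at Group A3 Day 29 and BD-Day 29.

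No actual bias can be calculated. The factors 1.05, 1.26 and 1.58 rest on an assumed 10-fold rise, assumed infected shares of 2%, 10% and 20%, and no waning; waning would reduce them. The change should be made before database lock, but the point does not invalidate the primary analysis.

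**What to change.** In SAP 5.2.3, 5.3.3 and 6.4:

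- Exclude from the PP immunogenicity summaries any sample taken on or after the first positive RT-PCR or nucleocapsid seroconversion after baseline (Part B: after the booster).
- Count any infection after the screen, not only those from 14 days after a dose as in the SAP 6.5 case definitions.
- Date a seroconversion at the first positive sample.
- Show the same PP Immunogenicity Set without this exclusion alongside. The mITT set is not a substitute, because it also differs in dosing, sampling and deviations. Keep the planned mITT analysis as it is.
- State how Memorandum 11 and the final deviation rules relate to this rule.

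The cost is SAP wording and one extra set of tables. Nucleocapsid serology is already drawn with the immunogenicity samples, and SAP 6.5.1.1 already defines an infection date that can be adapted. The downsides are fewer late samples and possibly informative censoring, which the paired presentation makes visible but does not remove.
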